4.3.2.4 Seroconversion

Not applicable.

4.3.2.5 Vaccine Response

Not applicable.

4.3.3 Efficacy

Not applicable.

4.3.4 Derived Other Variables

4.3.4.1 Age for Demographics

The age of a participant in the study will be the calendar age in years at the time of inclusion.

4.3.4.2 Study duration

The duration will be computed in days as follows:

Maximum (Visit dates [Visit 01 up to Visit 02], Termination date, Follow-up date, Last contact date) - min (V01 date) + 1

4.3.4.3 Participant Duration

The duration of a participant participation in the study will be computed as follows:

Maximum (Visit dates (Visit 01 up to Visit 02), Termination date (if prematurely withdrawn after vaccination), Follow up date, Last contact date) - Visit 01 date + 1.

5 Statistical Considerations

5.1 Statistical Hypotheses

No hypotheses will be tested. The analyses will be descriptive.

5.2 Sample Size Determination

The number of participants is designed to provide immunogenicity and safety data on the 3 SP0202 formulations and on Prevnar 13 and Pneumovax 23 after one injection in healthy adults aged 50 to 84 years.

The sample size was set to approximately 150 participants per group (approximately 75 by age group). Assuming a drop-out rate of approximatively 15%, a total of 128 evaluable participants per group by vaccine group is expected for the Per-Protocol Analysis Set (PPAS).

The expected precision of estimation for quantitative data is as follows (PPAS) - the maximum distance from the \log_{10} mean to the limits of 95% CI (confidence interval) is equal to 0.173 for single mean and 0.246 for difference in means of two groups (when the standard deviation is 1).

Standard deviation	N evaluable	Distance between \log_{10} mean and 95%CI limits for a single mean	Distance between 2 groups difference in \log_{10} means and 95%CI limits	Distance between GMT and 95%CI limits for a single mean	Distance from GMT ratio between 2 groups to 95%CI upper limit
0.5	128	0.087	0.123	1.22	1.33
0.6	128	0.104	0.148	1.27	1.41
0.7	128	0.121	0.172	1.32	1.49
0.8	128	0.139	0.197	1.38	1.57
0.9	128	0.156	0.222	1.43	1.67
1	128	0.173	0.246	1.49	1.76

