9.4.1 General Considerations

All analyses will be descriptive.

For immunogenicity data, assuming that log10 transformation of the titers / concentrations and titers / concentrations ratio follows a normal distribution, first, the mean and 95% confidence intervals (CIs) will be calculated on log10 (titers / concentrations; titers / concentrations ratio) using the usual calculation for normal distribution, then antilog transformations will be applied to the results of calculations, to compute geometric mean titers / concentrations (GMTs / GMCs) and geometric mean of the individual titer / concentration ratios (GMTRs / GMCRs) and their 95% CIs.

The 95% CIs of ratio of GMTs / GMCs between 2 groups will be computed from the difference of log 10 transformed means of titers/concentrations using normal approximation.

The 95% CIs of point estimates will be calculated using the exact binomial distribution (Clopper-Pearson method (29)) for proportions.

Generally, no replacement of missing data will be done.

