9.4.3 Immunogenicity Analyses

All immunogenicity analyses will be performed on the PPAS and presented by group and age group. Additional immunogenicity analyses will be performed on the FAS.

The point estimates and their 95% CI of at least the following parameters will be presented before and 1-month post-vaccination for each pneumococcal serotype specific OPA titers and IgG concentrations:

- GMT/GMC of serotype specific titers/concentrations
- GM of titers/ concentrations ratio (post- / pre-vaccination)

Differences in terms of ratio of GMTs/GMCs between 2 groups (ie, any SP0202 formulations and Prevnar 13 or Pneumovax 23) post-vaccination will be presented.

Reverse cumulative distribution curves (RCDCs) of individual concentrations/titers will be presented for all serotypes at pre and post-vaccination.

Missing data will not be imputed. No test or search for outliers will be performed.

For the calculation of GMTs / GMCs and percentage above cut-offs, any pre-vaccination or post-vaccination value reported as < LLOQ will be converted to a value of 0.5 LLOQ.

For the calculation of GMTR / GMCR, any pre-vaccination value reported as < LLOQ will be converted to LLOQ, and any post-vaccination value reported as < LLOQ will be converted to a titer of 0.5 LLOQ when only either the numerator or the denominator is < LLOQ. If both

numerator and denominator are < LLOQ, then both will be converted in the same way so that the increase is defined as 1.

Any value reported as > ULOQ (upper limit of quantitation) will be converted to ULOQ.

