5.4 Statistical Analyses

5.4.1 General Considerations

The statistical analyses will be performed under the responsibility of the Sponsor's Biostatistics platform using SAS® Version 9.4 software or later.

The results of the statistical analysis will be available in the final clinical study report (CSR).

For descriptive purposes, the following statistics will be presented:

Table 5.1: Descriptive statistics produced

Baseline characteristics and follow-up description	Categorical data	Number of participants. Percentage of participants.
	Continuous data	Mean, standard deviation, median, quartiles, minimum, and maximum.
Clinical safety results	Categorical data	Solicited: Number and percentage (95% CIs) of participants. Unsolicited: Number and percentage (95% CIs) of participants, and number of events.
Immunogenicity results	Categorical data (threshold, fold-rise)	Number and percentage (95% CIs) of participants.
	Continuous data (titer / data)	Log10: Mean and standard deviation. Anti-Log10 (work on Log10 distribution, and anti-Log10 applied): Geometric mean, 95% CI of the geometric mean, quartiles, minimum, and maximum. Graphical representation by Reverse Cumulative Distribution Curve (RCDC). Boxplots and Forest plots.

The CI for the single proportion will be calculated using the exact binomial method (Clopper-Pearson method, quoted by Newcombe (2)), ie, using the inverse of the beta integral with SAS.

For immunogenicity results, assuming that \log_{10} transformation of the titers / concentrations follows a normal distribution, at first, the mean and the 95% CI will be calculated on \log_{10} (titers / data) using the usual calculation for normal distribution (using Student's t distribution with $n-1$ degree of freedom), then antilog transformations will be applied to the results of calculations, in order to provide geometric means (GMs) and their 95% CI.

CIs of ratio of GMTs / GMCs between 2 groups will be computed from the difference in means of \log_{10} transformed titers/concentrations between 2 groups with normal approximation.

Disposition, demographics, medical history, and concomitant medications data will be summarized using counts and percentages.

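### Do the precision figures in the sample-size section understate the width of the planned confidence intervals, above all in the two age groups?

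*SAP*

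**What the plan says.** Neither document has a powered hypothesis; the support for the sample size is a table of expected precision, identical in SAP 5.2 and Protocol 9.2. Its starting point is "approximately 150 participants per group (approximately 75 by age group"), followed by "Assuming a drop-out rate of approximatively 15%, a total of 128 evaluable participants per group by vaccine group is expected". The table varies only the standard deviation, from 0.5 to 1, and every row has 128 evaluable. The lead-in sentence takes the largest values from it: on the log10 scale the half-width "is equal to 0.173 for single mean and 0.246 for difference in means of two groups (when the standard deviation is 1"). On the fold scale the same row reads 1.49 for a single geometric mean and 1.76 for a ratio.

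The analysis methods are set out elsewhere. SAP 5.4.1 gives the interval for a single mean "using Student's t distribution with" n-1 degrees of freedom, and the interval for a ratio from the difference in log10 means "between 2 groups with normal approximation". Protocol 9.4.1 says the ratio interval is "computed from the difference of log 10 transformed means of titers/concentrations using normal approximation"; for a single mean it refers only to the usual normal-theory calculation and does not name t.

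On presentation, Protocol 9.4.3 states: "All immunogenicity analyses will be performed on the PPAS and presented by group and age group". SAP 5.4.3 and Table 5.2 carry this through. Geometric means, post/pre ratios and all between-group ratios appear for all participants, for 50-64 years and for 65-84 years.

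**The concern.** The table is the trial's only quantitative support for its size, so it should describe the intervals that will be reported. It departs from them in two ways.

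First, its two half-width columns use the reverse of the distributions that SAP 5.4.1 assigns to them.

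Second, two of the three presentations of each immunogenicity endpoint are age-group results. Age is a randomization stratum, and the sample-size paragraph itself mentions about 75 per age group. Yet the table stops at the whole vaccine group, and the lead-in sentence uses the word maximum. A reader who took 0.246 (1.76-fold) as the worst case for any planned ratio would expect too much precision from the results in participants aged 65-84 years.

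**Working it through.** **Inputs.** 150 randomized per vaccine group, about 75 per age group and 15% drop-out (SAP 5.2); two-sided 95% intervals; SD 0.5 to 1 (table in SAP 5.2). Evaluable per vaccine group: 150 × 0.85 = 127.5, taken as 128. Evaluable per age group: 75 × 0.85 = 63.75, taken as 64. The second figure assumes the same loss in both age groups; the documents give no loss by age.

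**Formulas.** Single mean: q × SD / √n. Difference of two means: q × SD × √(2/n). Here q is either the normal quantile 1.960 or the t quantile on n-1 (single) or 2n-2 (difference) degrees of freedom.

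**Reproducing the plan's figures (n = 128, SD 1).**

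| | Normal quantile | Student's t | Stated |
|---|---|---|---|
| Single mean | 1.960/√128 = 0.1732 | 1.979/√128 = 0.1749 (127 df) | 0.173 |
| Difference | 1.960 × √(2/128) = 0.2450 | 1.969 × √(2/128) = 0.2462 (254 df) | 0.246 |

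The other rows show the same pattern.

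- Single mean, SD 0.6, 0.7, 0.8, 0.9: the stated 0.104, 0.121, 0.139, 0.156 match the normal quantile. Student's t gives 0.105, 0.122, 0.140, 0.157.
- Difference, SD 0.6, 0.8, 0.9: the stated 0.148, 0.197, 0.222 match t. The normal quantile gives 0.147, 0.196, 0.220.
- Using the normal quantile with n = 127 does not explain the table: it gives 0.246 for the difference at SD 1, but 0.174 for the single mean.

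So the columns are indeed swapped relative to SAP 5.4.1.

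**Size of the swap at SD 1.** Single mean: 0.173 becomes 0.175, and the factor goes from 1.49 to 1.50. Difference: 0.246 becomes 0.245, and the factor stays at 1.76 (10^0.2450 = 1.758; 10^0.2462 = 1.763).

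**Age groups, with the SAP 5.4.1 methods (n = 64, SD 1).**

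- Single mean: 1.998/√64 = 0.250, a factor of 10^0.2498 = 1.78. Against 0.173 this is 0.2498/0.173 = 1.44, or 44% wider.
- Difference: 1.960 × √(2/64) = 0.346 (0.3465 to four decimals), a factor of 2.22. Against 0.246 this is 0.3465/0.246 = 1.41, or 41% wider.
- Range over n: 0.252 and 0.349 at n = 63; 0.230 and 0.320 with no loss (n = 75).
- Range over SD at n = 64: from 0.125 and 0.173 at SD 0.5 to the figures above at SD 1.

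**Does the table claim to cover age groups?** The sentence with the word maximum is qualified by SD = 1 and introduces a table in which SD is the only input that varies. Maximum therefore means the row with the largest SD. The evaluable number, 128, is tied to the vaccine group in the sentence before and repeated in every row. No age-group figure is stated, so none is misstated. Because the approximate size of each age group is given in the same paragraph, a reader can scale: halving n multiplies the half-width by about √2, and 0.246 × 1.414 = 0.348, close to the 0.346 above.

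**The case for a change.** The strongest case for a change is that the age groups are no afterthought. They are randomization strata with a stated size, and all nine between-group ratios in SAP Table 5.2 are repeated in each. The lead-in sentence speaks of precision for quantitative data without limiting itself to all participants, directly after the split by age. On the sponsor's own inputs, age-group ratios pass 0.246 already at SD 0.8 (0.277) and SD 0.9 (0.312). Even with no drop-out the SD 1 figure is 0.320, so the gap does not hang on the 15%. Adding rows for 64 evaluable would cost little.

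The arithmetic stands, and such rows would be informative. What does not follow is that something in the plan is wrong or that a result would change. The table is right to within 0.002 for the number it is labelled with, and the wider age-group intervals will be visible in the results themselves.

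The complaint about distributions is also softer than it looks. SAP 5.4.1 describes its t interval as a normal-distribution calculation, so a normal approximation for ratios may mean normality of the log10 values rather than the normal quantile. Since Protocol 9.4.1 does not name t for single means, the clear mismatch is the single-mean column of the SAP: 0.173 against 0.175.

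**Conclusion.** No change follows. The swap of distributions is a clerical slip that moves the SD 1 half-widths by at most 0.002 on the log10 scale and leaves the ratio factor at 1.76. The missing age-group precision is an omission from a planning table, not a false figure: about 0.250 (1.78-fold) for a single mean and 0.346 (2.22-fold) for a between-group difference, given SD 1 and about 64 evaluable per age group at an equal 15% loss.

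Nothing depends on either point. Protocol 9.1 and SAP 5.1 make the trial descriptive, and Protocol 9.2 states that there is no formal sample-size computation. No margin, success criterion or formulation-selection rule draws on these half-widths. The analysis methods are fixed in SAP 5.4.1 whatever the planning table used, so the reported intervals will be computed from the actual numbers and observed variability in each age group. Revising the table would change neither enrolment, nor an analysis, nor a conclusion.

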5.3 Population for Analyses

Population	Description
Randomized	All participants with data in the CRF
Safety Analysis Set (SafAS)	Participants who have received the study vaccine. All participants will have their safety analyzed according to the vaccine they actually received. Safety data recorded for a vaccine received out of the protocol design will be excluded from the analysis (and listed separately).
Full analysis set (FAS)	Subset of randomized participants who received at least 1 dose of the study vaccine and had a valid post-vaccination blood sample result (serotype specific IgG concentration or serotype specific OPA titer for at least one serotype). Participants will be analyzed according to the intervention to which they were randomized.
Per-protocol analysis set (PPAS)	
Subset of the FAS. Participants presenting with at least one of the following relevant protocol deviations will be excluded from the PPAS:
 
 • Participant did not meet all protocol-specified inclusion criteria or met at least one of the protocol-specified exclusion criteria • Participant did not receive vaccine • Participant received a vaccine other than the one that he / she was randomized to receive • Preparation and / or administration of vaccine was not done as per-protocol • Participant did not provide the post-dose serology sample at V02 in the proper time window or a post-dose serology sample was not drawn • Participant received a protocol-prohibited therapy / medication / vaccine 
In addition to the reasons listed above, participants will also be excluded from the PPAS if their Visit 02 / post-vaccination serology sample did not produce a valid test result (ie, results for all pneumococcal serotypes for both OPA and IgG are missing).
 
In the event of a local or national immunization program with a pandemic influenza vaccine, participants who receive 1 or more doses of a pandemic influenza vaccine at any time during the study will not be withdrawn from the study.
 
As the COVID-19 vaccination campaign has been deployed during the study period, participants who receive 1 or more doses of COVID-19 vaccine during the study period will not be withdrawn from the study.

5.4 Statistical Analyses

5.4.1 General Considerations

The statistical analyses will be performed under the responsibility of the Sponsor's Biostatistics platform using SAS® Version 9.4 software or later.

The results of the statistical analysis will be available in the final clinical study report (CSR).

For descriptive purposes, the following statistics will be presented:

Table 5.1: Descriptive statistics produced

Baseline characteristics and follow-up description	Categorical data	Number of participants. Percentage of participants.
	Continuous data	Mean, standard deviation, median, quartiles, minimum, and maximum.
Clinical safety results	Categorical data	Solicited: Number and percentage (95% CIs) of participants. Unsolicited: Number and percentage (95% CIs) of participants, and number of events.
Immunogenicity results	Categorical data (threshold, fold-rise)	Number and percentage (95% CIs) of participants.
	Continuous data (titer / data)	Log10: Mean and standard deviation. Anti-Log10 (work on Log10 distribution, and anti-Log10 applied): Geometric mean, 95% CI of the geometric mean, quartiles, minimum, and maximum. Graphical representation by Reverse Cumulative Distribution Curve (RCDC). Boxplots and Forest plots.

The CI for the single proportion will be calculated using the exact binomial method (Clopper-Pearson method, quoted by Newcombe (2)), ie, using the inverse of the beta integral with SAS.

For immunogenicity results, assuming that \log_{10} transformation of the titers / concentrations follows a normal distribution, at first, the mean and the 95% CI will be calculated on \log_{10} (titers / data) using the usual calculation for normal distribution (using Student's t distribution with $n-1$ degree of freedom), then antilog transformations will be applied to the results of calculations, in order to provide geometric means (GMs) and their 95% CI.

CIs of ratio of GMTs / GMCs between 2 groups will be computed from the difference in means of \log_{10} transformed titers/concentrations between 2 groups with normal approximation.

Disposition, demographics, medical history, and concomitant medications data will be summarized using counts and percentages.

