6.3 Measures to Minimize Bias: Randomization and Blinding

6.3.1 Randomization and Allocation Procedures

This study will be a randomized, modified double-blind study for 5 vaccine groups.

On the day of enrollment, participant who meet the inclusion/exclusion criteria and sign the informed consent form (ICF) will be randomly assigned to Groups 1 through 5 in a 1:1:1:1:1 ratio, stratified according to sites and age group such that each group will have approximately 150 participants (around 75 participants aged 50 to 64 years and around 75 participants aged 65 to 84 years).

The unblinded vaccinator or delegate will connect to the IRT, enter the identification and security information, and confirm a minimal amount of data in response to IRT prompts. The IRT will then provide the group assignment and have the site staff confirm it. The full detailed procedures for group allocation are described in the Operating Guidelines. If the participant is not eligible to participate in the study, then the information will only be recorded on the participant recruitment log.

Participant numbers that are assigned by the IRT will consist of a 12-digit string (a 3-digit country identifier, a 4-digit study center identifier, and a 5-digit participant identifier). The first digit of the participant identifier will be “1” for participants aged 50 to 64 years and “2” for participants aged 65 to 84 years. For example, Participant 840000210005 is the fifth participant aged 50 to 64 years enrolled in Center Number 2 in the US (840 being the US code country).

Participant numbers should not be reassigned for any reason. The randomization codes will be kept securely in the IRT and an internal system.

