Sanofi Pasteur is developing a multivalent pneumococcal conjugate vaccine (PCV, henceforth referred to as SP0202) that would extend the protection against pneumococcal disease to serotypes 8, 9N, 10A, 11A, 12F, 15B, 22F, and 33F, in addition to the 13 serotypes included in Prevnar 13® (1, 3, 4, 5, 6A, 6B, 7F, 9V, 14, 18C, 19A, 19F, and 23F). These serotypes have been selected based on recent epidemiological data that showed increasing emergence in North America and in Europe.

PSK00009 is a Phase II study that will evaluate the immunogenicity and safety of 3 SP0202 formulations administered as a single dose to healthy adults aged 50 to 84 years naïve to prior pneumococcal vaccine administration. Two groups will serve as controls and receive a single dose of either Prevnar 13 or Pneumovax 23®. In this study, Prevnar 13 will serve as a reference vaccine for safety assessment and for immunogenicity of the 13 common serotypes with SP0202. Pneumovax 23 will provide a reference for the immune response to the 8 additional serotypes in SP0202 formulations.

The SP0202 investigational vaccine is intended to provide protection against invasive and non-invasive diseases caused by the *Streptococcus pneumoniae* serotypes included in the vaccine, in population from infants to elderly.

2 Trial Objectives

Objectives
Immunogenicity To assess the immune response of the 3 SP0202 formulations, Prevnar 13, and Pneumovax 23, 30 days after the administration of the single dose vaccination
Safety To assess the safety profile of the 3 SP0202 formulations, Prevnar 13, and Pneumovax 23

3 Description of the Overall Trial Design and Plan

Overall Design

Type of design	Parallel, multicenter (approximately 8 sites)
Phase	II
Control method	Active-controlled (controls = Prevnar 13 and Pneumovax 23)
Study population	Healthy adults aged 50 to 84 years
Countries	United States of America
Level and method of blinding	Modified double-blind (observer-blind)
Study intervention assignment method	Randomization with stratification by sites and age groups (ie, 50-64 years and 65 to 84 years)
Review group	Safety Management Team (SMT) and Data Monitoring Committee

Disclosure Statement:

This is a parallel group prevention study with 5 groups that is Participant, Investigator and Outcomes Assessor blinded.

Number of Participants:

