5.4.3 Immunogenicity Analyses

The immunogenicity analyses will be performed first on the PPAS and then on the FAS.

The point estimates and their 95% CI of the following parameters will be presented by group for all participants and by age group before and one month post-vaccination for each pneumococcal serotype specific OPA titers and IgG concentrations:

- GMT/GMC of serotype specific titers/concentrations.
- GMT/GMC ratio (post/pre-vaccination).

In addition, the following analyses will be presented:

- Differences in terms of ratio of GMTs/GMCs between 2 groups (for instance, any SP0202 formulations and Prevnar 13 or Pneumovax 23) and 95% CI at 1-month post-vaccination on all participants and by age group.
- Percentages of participants with titers/concentrations above certain thresholds and achieving several X-fold from pre to post-vaccination.
- Several graphical representations (in a log10 scale) will be used for all serotypes by group for all participants and by age group:
 - RCDCs of individual OPA titers and IgG concentrations at pre and 1-month post-vaccination.
 - Forest plots of GMTs or GMCs at pre and 1-month post-vaccination.
 - Forest plots of GMT/GMC ratio between groups at 1-month post-vaccination.
 - Boxplots of the OPA titers and IgG concentrations at pre and 1-month post-vaccination.

Table 5.2: Summary of statistical analyses for immunogenicity analysis

Endpoint	Visit and Age group	Description
Serotype-specific pneumococcal OPA titer for each of the 21 serotypes	V01 and V02 - all participants	OPA GMT and 95% CI, corresponding Forest Plot
	V01 and V02 - 50-64 years	
	V01 and V02 - 65-84 years	
	V02/V01 - all participants	OPA GMT ratio (post/pre) and 95% CI
	V02/V01 - 50-64 years	
	V02/V01 - 65-84 years	
	V02/V01 - all participants	Percentage of participants with titers at V02 \geq 2/4/8/16-fold rise over V01 and 95% CI and <LLOQ at V01 to \geq LLOQ at V02
	V02/V01 - 50-64 years	
	V02/V01 - 65-84 years	
	V02 - all participants	OPA GMT ratio and 95% CI and corresponding Forest Plot between:
	V02 - 50-64 years	
 - each SP0202 formulation (ie, SP0202-VI/SP0202-IIb, SP0202-VII/SP0202-IIb, SP0202-VII/SP0202-VI) - any SP0202 group and Prevnar 13 or Pneumovax 23 (ie, SP0202-IIb/Prevnar 13, SP0202-VI/Prevnar 13, SP0202-VII/Prevnar 13; SP0202-IIb/Pneumovax 23, SP0202-VI/Pneumovax 23, SP0202-VII/Pneumovax 23)
	V02 - 65-84 years	
	V01 and V02 - all participants	OPA titer RCDC
	V01 and V02 - 50-64 years	

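### The all-participant GMT/GMC ratios and their CIs carry no term for site or age group, the factors that randomisation is stratified by; adding them is a near-free gain whose size depends on how prognostic they are

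*SAP*

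**What the plan says.** Design. SAP section 3 describes "Randomization with stratification by sites and age groups (ie, 50-64 years and 65 to 84 years"), at approximately 8 sites. Protocol 6.3.1 has participants allocated 1:1:1:1:1, "stratified according to sites and age group such that each group will have approximately 150 participants", with around 75 in each age group.

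Between-group ratio. Protocol 9.4.1: "The 95% CIs of ratio of GMTs / GMCs between 2 groups will be computed from the difference" of mean log10 values, with a normal approximation. SAP 5.4.1 repeats the rule: "CIs of ratio of GMTs / GMCs between 2 groups will be computed from the difference in means of" log10-transformed titres or concentrations. Neither names age group, site or stratum weights. SAP 5.4.3 shows the ratios "at 1-month post-vaccination on all participants and by age group", first on the PPAS and then on the FAS.

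Adjusted analysis. SAP 5.4.4 plans a cLDA that brings in the baseline titre or concentration. It is on the FAS only, goes to a CSR appendix, and names neither age group nor site.

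Precision. SAP 5.2: "Assuming a drop-out rate of approximatively 15%, a total of 128 evaluable participants per group by vaccine group is expected" for the PPAS. The largest 95% CI half-width on the log10 scale "is equal to 0.173 for single mean and 0.246 for difference in means of two groups (when the standard deviation is 1"). The analyses are descriptive and no hypotheses are tested (Protocol 9.1, SAP 5.1).

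**The concern.** Stratified allocation gives the arms nearly the same mix of sites and ages, so differences between strata largely cancel when two arms are compared. The planned CI uses each arm's raw SD, which still contains those differences. If age or site predicts the titre, the CI is wider than the design requires.

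If PPAS exclusions leave two arms with different age mixes, the unadjusted ratio also picks up part of the age effect.

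This matters even without hypotheses, because CI precision is the only quantitative argument for the sample size. The formula also feeds many results: 9 pairwise contrasts x 21 serotypes x 2 assays = 378 all-participant ratios per analysis set. Protocol 2.1 says that the three formulations are meant to secure the choice of a lead for Phase III, and these ratios compare them. Protocol 2.2 gives some reason to expect an age effect, since it lists adults over 65 among those in whom polysaccharide vaccines are least immunogenic. It gives no figure.

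**Working it through.** **1. Reproduce the plan's precision** (inputs from SAP 5.2).

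- Evaluable per group: 150 x 0.85 = 127.5, taken as 128.
- Single mean, SD 1: 1.96 x 1/sqrt(128) = 0.173.
- Difference, SD 1: t(254 df) x sqrt(2/128) = 0.246, a ratio factor of 10^0.246 = 1.76. Using z gives 0.245.

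All six SD rows reproduce in this way, including the lowest, "0.5 128 0.087 0.123 1.22 1.33". No stratum term is needed, so the stated precision is the plain two-sample one.

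**2. Effect of age stratification on the CI.** Let D be the difference in mean log10 titre between the age groups. The documents do not give D; 0.1 to 0.5 is assumed. With a 50:50 age split and the total SD as in SAP 5.2, the within-age SD is sqrt(SD^2 - D^2/4) and the half-width is 1.96 x SD x sqrt(2/128).

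| Total SD | Plain | D = 0.1 | D = 0.2 | D = 0.3 | D = 0.5 |
|---|---|---|---|---|---|
| 0.5 | 0.1225 | 0.1219 (-0.5%) | 0.1200 (-2.0%) | 0.1169 (-4.6%) | 0.1061 (-13.4%) |
| 0.7 | 0.1715 | 0.1711 (-0.3%) | 0.1697 (-1.0%) | 0.1675 (-2.3%) | 0.1602 (-6.6%) |
| 1.0 | 0.2450 | 0.2447 (-0.1%) | 0.2438 (-0.5%) | 0.2422 (-1.1%) | 0.2372 (-3.2%) |

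Read as excess width, the largest value at D = 0.3 is 0.1225/0.1169 = 1.048, or 4.8%.

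**3. Age and site together** (site SD also assumed). Plain over stratified width is sqrt(SDw^2 + D^2/4 + SDsite^2)/SDw, where SDw is the within-stratum SD.

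- D 0.3, SDw 0.6, site SD 0.1: sqrt(0.36 + 0.0225 + 0.01)/0.6 = 1.044.
- D 0.4, SDw 0.5, site SD 0.2: sqrt(0.25 + 0.04 + 0.04)/0.5 = 1.149.

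**4. Simulation with random 15% loss.**

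- Age only, fixed total SD, 100,000 runs: the plain CI covers 95.0% (SD 0.5, D 0.1), 95.8% (SD 0.5, D 0.3), 97.2% (SD 0.5, D 0.5), 95.3% (SD 0.7, D 0.3) and 95.1% (SD 1, D 0.3). The age-stratified CI covers 94.8% to 94.9%.
- With sites, for the two settings in step 3: the plain CI covers 96.1% and 97.0% and is 3.5% and 13% wider than the stratified CI.
- With no stratum effect, the plain CI is about 1% narrower than the stratified one.

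**5. Age imbalance in the PPAS.** A gap in age share between two arms shifts the log10 ratio by gap x D.

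- Chance: random 15% loss from 75 per age group gives a gap with SD 2.4 points; 95% of gaps are below 4.8 points. A 5-point gap at D 0.3 multiplies the ratio by 10^(0.05 x 0.3) = 1.035.
- Cover for chance: the plain formula keeps an age variance of (D^2/4) x (2/128) = 0.0039 D^2. Chance imbalance needs 0.024^2 x D^2 = 0.0006 D^2. The plain CI more than covers it.
- Systematic loss (assumed): one arm loses 10% of one age group and 20% of the other, and a second arm the reverse. The shares are 67.5/127.5 = 52.9% and 60/127.5 = 47.1%, a gap of 5.9 points. At D 0.3 the ratio moves by 10^(0.059 x 0.3) = 1.04. The CI does not allow for this part.

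**The case against.** A reader might infer three stronger things, and the documents support none of them.

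- **That the CIs are too wide as a matter of fact.** This needs prognostic strata, and no age or site effect on titre is given. Protocol 2.2 is qualitative and concerns polysaccharide vaccines. Each assay is run in one laboratory (Protocol 8.1.2), so sites add no between-laboratory variation, and previously vaccinated people are excluded (Protocol 5.2, E04). A site SD of 0.2 is purely an assumption.
- **That PPAS age imbalance is an uncovered error in the ratio.** The two harms partly offset: the age variance that widens the plain CI is also what covers chance imbalance. Only loss that differs by both age and vaccine is left, and nothing in the documents points to it.
- **That the trial falls short of its stated precision.** The stated figures are the plain two-sample ones, so the planned analysis delivers them. Any departure from 95% coverage due to balanced strata is on the safe side.

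The plan also has partial safeguards. Every ratio is repeated within each age group, where imbalance between the two age groups cannot enter. The FAS repeat removes imbalance caused by PPAS exclusions. The cLDA adds a baseline-adjusted ratio.

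All of this limits the size of the point. It does not remove it: the by-age ratios do not change the pooled estimate or its CI, the cLDA is not planned on the PPAS and is not said to include the strata, and no reason is given for leaving them out.

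**Conclusion.** The omission is clear from the text. Its consequence is conditional and usually small.

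- For age effects up to 0.3 log10 and SDs of 0.5 to 1.0, the all-participant CI is under 5% too wide.
- About 13-15% requires strong stratum effects with an SD near 0.5, for example an age effect of 0.4 with a site SD of 0.2.
- If the strata are not prognostic, nothing is gained and about 1% of width may be lost.
- Systematic PPAS loss of the kind assumed above would move the ratio by about 4% at an age effect of 0.3. That is small beside the planned CI factors of 1.33 to 1.76, and the by-age and FAS results would partly reveal it.

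All stratum effects here are assumptions. No type I error, power or decision rule is affected. This is a free improvement to a descriptive analysis, not a demonstrated error. It is still worth making, because CI precision is the plan's own rationale for its sample size.

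**What to change.** In SAP 5.4.1 and 5.4.3, for each all-participant pairwise contrast:

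- Fit a linear model to log10 titre or concentration in the two groups compared, with vaccine group, age group and site as factors. Pool small sites by a rule fixed in advance.
- Allow the residual variance to differ by group. Equal variance is doubtful, for instance, for the 8 serotypes that Prevnar 13 does not contain.
- Take the ratio and 95% CI from the back-transformed group contrast.
- Keep the simple two-sample ratio as a supportive output.

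In SAP 5.4.4, state that the FAS cLDA includes age group and site.

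Cost: a few SAP lines and a model statement. Both factors are already held for randomisation. With 8 sites they use 1 + 7 = 8 degrees of freedom; with the intercept and group term, 256 - 10 = 246 remain.
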